## **Methods**

### **Study design**

The present study adopts quasi-experimental design. To avoid contamination between participants in two study arms, cluster sampling is used. Patients with T2DM of an endocrinology clinic in southern Taiwan are assigned to the intervention arm, whereas patients at another endocrinology clinic in southern Taiwan are placed in the control arm. Eligible patients that match the inclusion criteria are recommended by doctors to initiate insulin treatment after getting the consent forms from eligible participants. Research assistants will subsequently collect baseline data from eligible participants. Afterwards, the participants in the intervention arm will receive the intervention. For the control arm, the participants will receive regular patient education originally administered at the hospital. Data for the participants in both study arms will be collected by research assistants at baseline, 3 months, 6 months, and 12 months post-intervention. The main outcome variable is change in HbA1c levels, while the change in stage of change, in insulin injection adherence, in appraisal of insulin injection, in patient empowerment, in self-efficacy for insulin injection, in diabetes distress, in quality of life, in triglyceride(TG), in total cholesterol (TC), in high-density lipoprotein cholesterol(HDL-C), in low density lipoprotein cholesterol(LDL-C), in urine albumin creatinine ratio (UACR), in estimated glomerular filtration rate(GFR) are secondary outcome variables. The outcome

variables and collection time points are summarized in Table 1.

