### *Demographic data & disease characteristics*

Age, sex, educational level, duration of diabetes, duration of taking oral drug before insulin therapy will be collected at baseline. Insulin treatment regimen including type of insulin, dose, frequency of injection and blood sugar self-monitoring will be collected after participants receiving insulin injection.

*Stage of change for insulin injection.* A question of stages of change for insulin injection was developed. At baseline, the question was “If the doctor recommends that you initiate insulin treatment right now, what would be your opinion?” Three responses to this question included “never considered”, “under consideration and might start within the next 6 months”, and “likely to start immediately”, which respectively represented three early stages of change — precontemplation, contemplation, and preparation. At the 3, 6, and 12 months post-intervention, the question was “what’s the status of your insulin injection?” The responses were “taking insulin injection previously, but now is stop insulin injection and never consider to receive insulin injection again”, “taking insulin injection previously, but now is stop insulin injection, consider to start insulin injection again within next 6 months”, “still receive insulin injection but sometimes forget to inject” , “Continuously inject insulin but less than 6 months”, “Continuously injected insulin and more than 6 months”.

*Insulin injection adherence.* An 8-item Morisky Medication Adherence Scale was used to assess insulin injection adherence behaviors of participants. The total scores ranged from 7 to 11. The higher scores indicate, the better insulin injection adherence behaviors

*Appraisal of insulin injection.* A 13-item Decisional Balance for Insulin Injection scale was used in the study to assess the appraisal of insulin injection. The scale comprised subscales of positive and negative appraisal. Each item was rated from 1 (strongly

disagree) to 5 (strongly agree). Decisional balance for insulin injection was calculated by deducting the mean score of positive appraisal with that of negative appraisal. The higher score indicated the higher decisional balance for insulin injection.

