### **Usual care of the control arm**

Participants in the control arm attend regular patient education at the hospital.

The contents of the education plan are as follows:

1. Teach participants the method of injection following the standard procedure, including gathering insulin supplies, the steps of injection, and so on.
2. Hand out a step-by-step pictorial guide to participants after teaching them the techniques and supply preparation for using insulin pen. Fill in the type and dose of insulin and the site and time of injection on a sheet for participants and their family to refer to after they return home.
3. Recommend patients to administer blood-glucose self-monitoring and record the results.
4. Conduct a telephone follow-up 3 days after patient education to check on the condition of insulin injection. Schedule a return visit after a week, during which the doctor adjusts the medication according to the results of SMBG and instructs the rule for dose adjustment at home.
5. Provide a hotline for patients to seek consultation when they encounter difficulties or problems.
6. Play patient education video clips on insulin injection in the waiting room when patients come for return visits.

7. Provide patient education in small groups occasionally, in which insulin-treated patients are invited to share their experience and clarify questions.

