	
think about the relationship between insulin injection, diet, and physical activity
 
 
• Provide patient education on blood-glucose self-monitoring and assessment on the ability to deal with hypoglycemia
 
• Ask patients to continuously keep a daily record of the dose, time, site of injection, administration of blood-glucose self-monitoring, and incidents of hypo/hyperglycemia in the “Health Guardian Pamphlet”
 
	
Action	
 
• Educate family members to provide support for patients
 
• Build an instant online interactive system with professionals to provide feedback to patients
 
	Helping relationship
	
 
• Encourage patients to adhere to the insulin injection plan
 
• Healthcare professionals conduct telephone interviews and schedule return visits for patients on a regular basis
 
• Instruct patients how to adjust their diet and exercise flexibly according to insulin injection so as to decrease the chance of termination caused by barriers
 
• Teach patients to adjust the dose of insulin according to the results of blood-glucose self-monitoring
 
	Reinforcement management
	
 
• Patients promise to set mid-term and long-term goals
 
	Self-liberation

---

[figure not shown]
Table 3. Motivational group activity

Stage of Change	Strategy	Process of Change
Precontemplation	
 
• Listen to fellow patients in the stages of action and maintenance share the benefits of insulin injection and the ways to overcome obstacles
 
• Try out insulin injection
 
• Use pictorial or multimedia materials to illustrate the relationship between insulin and blood-glucose
 
	Self-reevaluation
Preparation	
 
• Listen to fellow patients in the stages of action and maintenance share the benefits of insulin injection and the ways to overcome obstacles
 
• Try out insulin injection
 
• Use pictorial or multimedia materials to illustrate the relationship between insulin and blood-glucose
 
	Self-reevaluation
Action	
 
• Share experience in insulin injection and provide support and solution
 
• Build mutually supportive partnerships with fellow patients
 
	Reinforcement management

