Maintenance	
 
• Share successful experience with other patients to enhance the motivation of the patient to continue insulin injection
 
	Reinforcement management

Table 4. Insulin injection follow-up management

Stage of Change	Strategy	Process of Change
Preparation	
 
• Follow up problems with insulin injection, e.g. dose, site of injection, and technique
 
	Reinforcement management
Action	
 
• Guide patients to examine the relationship between insulin injection and changes in blood-glucose to strengthen their self-efficacy
 
	Self-reevaluation
	
 
• Ask patients to continuously keep a daily record of the dose, time, site of injection, administration of blood-glucose self-monitoring, and incidents of hypo/hyperglycemia in the “Health Guardian Pamphlet”
 
	Counterconditioning
Maintenance	
 
• Encourage patients regularly when HbA1c level decreases
 
• Provide care and support
 
	Reinforcement management

Figure 1. Intervention flowchart of the intervention arm

\* Motivational group activities are held once every two months. Patients in the stages of action and maintenance will be invited to share their experiences during the activity.

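### No hypoglycaemia outcome is described for either arm, so the trial cannot say whether a lower HbA1c came with more hypoglycaemia

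*Combined protocol and SAP*

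**What the plan says.** **Outcomes.** Study design states: "The main outcome variable is change in HbA1c levels". It then lists thirteen secondary outcomes: stage of change, six questionnaire scales, four lipids and two renal measures. None is hypoglycaemia or any adverse event. Table 1 has twelve rows, and none concerns hypoglycaemia or safety. Data Analysis describes no such variable.

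**Intervention arm.** Table 2 (Preparation) includes education with "assessment on the ability to deal with hypoglycemia". It also asks patients to keep a daily record in a pamphlet, covering among other things "administration of blood-glucose self-monitoring, and incidents of hypo/hyperglycemia in the" pamphlet. The Action row of Table 4 (the table captioned as follow-up management) repeats that request. Both entries are filed under counterconditioning, a process of change. Table 2 (Action) teaches patients to adjust their insulin dose from self-monitoring results.

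**Control arm.** Usual care, item 3, reads: "Recommend patients to administer blood-glucose self-monitoring and record the results". Under item 4, at the one-week visit "the doctor adjusts the medication according to the results of SMBG" and "instructs the rule for dose adjustment at home". None of the seven items mentions hypoglycaemia.

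**Nearest data collected in both arms.** "Insulin treatment regimen including type of insulin, dose, frequency of injection and blood sugar self-monitoring will be collected after participants receiving insulin injection". This is regimen information, and no low-glucose threshold or episode count is given.

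**The concern.** Doctors recommend insulin to eligible patients in both clinics, and both arms are taught to adjust the dose at home. The intervention is designed to raise uptake and adherence. If it succeeds, insulin exposure will be higher in that arm, and any fall in HbA1c has to be read beside its most direct possible cost.

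The plan measures HbA1c four times over 12 months and has no measure of hypoglycaemia on a common basis. A favourable HbA1c result could be reported with nothing to say about whether hypoglycaemia was more frequent. The only written record that could be turned to afterwards is the intervention pamphlet, which has no control-arm counterpart. A comparison built on it would mix true frequency with differences in recording.

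**Working it through.** **1. Where hypoglycaemia appears**

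| Place in the plan | Hypoglycaemia mentioned? | Arm |
|---|---|---|
| Study design, outcome list | No | both |
| Measurements (biomedical and questionnaire) | No | both |
| Table 1, 12 rows | No | both |
| Data Analysis | No | both |
| Table 2, Preparation | Yes: education item and daily record | intervention |
| Table 4, Action | Yes: daily record | intervention |
| Usual care, items 1 to 7 | No; self-monitoring results only | control |

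Study design gives data collection to the research assistants, in both arms, at baseline and at 3, 6 and 12 months. No section says that they collect or transcribe the pamphlet. The computerised system mentioned in the intervention plan serves the interveners and is not described as a source of outcome data. So the pamphlet is an intervention tool, and hypoglycaemia is a study variable in neither arm.

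**2. The plan's sample size**

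Inputs from Samples: standardised effect 0.5, α 0.05 (taken as two-sided), power 0.8.

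n per arm = 2 × (1.96 + 0.842)² / 0.5² = 62.8, so 63. This reproduces the plan's figure; a one-sided test would give 50. The plan's 76 is 63 × 1.2 = 75.6, rounded up. I use 63 below because it is the plan's own target for analysable participants.

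**3. What equal collection would give**

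The documents give no hypoglycaemia rate, so the risks here are assumptions. Take p as the proportion with at least one episode, equal in both arms. The 95% half-width for the risk difference is 1.96 × √(2p(1 − p)/63).

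- p = 0.10: 1.96 × √(0.18/63) = 10.5 points
- p = 0.20: 1.96 × √(0.32/63) = 14.0 points
- p = 0.30: 1.96 × √(0.42/63) = 16.0 points

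At 63 per arm, two-sided 0.05 and 80% power, the detectable rises are from 5% to about 22%, 10% to about 30%, 20% to about 43%, and 30% to about 55%.

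Episodes needing another person's help may be rarer, and the normal approximation is then poor. If none of 63 participants reported one, the one-sided 95% upper limit for the risk would be 1 − 0.05^(1/63) = 4.6%.

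A common measure would therefore give an estimate with a fairly wide interval. The plan as written gives none.

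**The case against.** **Existing data may be enough.** Self-monitoring information is collected in both arms once insulin starts. The quality-of-life scale touches on diabetes-specific symptoms. Control patients have a telephone call at 3 days, a visit at one week and a hotline. The questionnaire items are not reproduced, so one cannot say that the research assistants never ask about hypoglycaemia. That caution stands: the supportable statement is that no hypoglycaemia measure is described. But a regimen item without a threshold, a symptom domain inside a 0 to 60 total, and clinical contacts outside the data plan do not amount to an outcome.

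**The measure would be weak.** This is partly right. Recall misses mild episodes. It may also differ by arm even with identical questions, because intervention patients are taught about hypoglycaemia and keep a diary. With one clinic per arm, a difference cannot be separated from clinic. These points limit what may be claimed, but they do not justify having no measure.

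**Stronger readings that the documents do not support:**

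- A reader might infer that the study captures events in one arm and not the other, and so will show a false excess. No section makes the pamphlet study data. Any figure for such an excess would describe an unplanned comparison with invented rates.
- A reader might infer that the diary stops at Maintenance, since that row of Table 4 ("Encourage patients regularly when HbA1c level decreases", plus care and support) omits it. The request is for continuous daily recording, nothing says it ends, and a figure is missing after Table 2's Action row.
- A reader might infer that the plan declares hypoglycaemia a treatment risk. It mentions it only in an education item and in the diary request.

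**Conclusion.** The concern holds as an omission common to both arms. The plan describes no hypoglycaemia outcome, and the only written record of episodes belongs to the intervention. As written, the trial cannot say whether a lower HbA1c came with more hypoglycaemia, and the pamphlet cannot fill the gap without unequal ascertainment.

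The primary HbA1c analysis is unaffected. What is lost is the ability to read a benefit beside its possible harm, so this should be changed, although it does not invalidate the trial. The absence of a described measure is certain from the text. The precision figures are less certain: they rest on assumed risks of 10% to 30%, equal risks in the two arms, and 63 analysed per arm. Even with the change, the result would be a descriptive comparison of two clinics.

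**What to change.** **If data can still be collected:**

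- Add a hypoglycaemia row to Table 1 at 3, 6 and 12 months, collected by the research assistants with identical items in both arms. The items are: episodes since the last contact; episodes needing another person's help or emergency care; and, if insulin was stopped, whether hypoglycaemia was the reason.
- List it as a safety outcome in Study design.
- Report it by arm among all participants, with a confidence interval. Make episodes needing help the main comparison, since these should depend least on how often a patient tests or keeps a diary. Use an interval suited to small counts if they are rare.
- Do not restrict the comparison to those on insulin at the visit. Being on insulin is something the intervention changes, and the restriction would drop people who stopped because of hypoglycaemia.
- Keep the pamphlet as an intervention tool and base no between-arm statement on it.
- State the limits: recall that may differ by arm, confounding with clinic, and wide intervals.

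**If collection is already complete** (Data Analysis is in the past tense, so this is unclear), state that hypoglycaemia was not comparably measured and make no between-arm safety claim.

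**Cost.** About three questions at contacts that both arms already have, slight respondent time, one table row, and an amendment at two ethics committees. No added staff, visits or procedures.
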